### Measurement of Primary Outcomes:

Our primary quantitative outcomes will be change in parents' HPV vaccine intentions (Aim 2) and adolescent HPV vaccine uptake (Aims 1-3). Medical records will be reviewed after 12 months to ascertain HPV vaccine status. Medical records will also be reviewed for receipt of three other adolescent vaccines (TDAP, MCV4, and influenza) as well as number and location of primary care visits in the 2 years prior to study participation.

The baseline survey will be administered to all enrolled parents (n=369) after or at the end of the recruitment call by a trained research assistant (RA), except for Aim 3 participants. The self-persuasion interview data (Aims 1A & 2), exit interviews (Aims 1-3), and audiorecorded parent-provider discussions (Aims 1B & 3) will be collected in-person by a trained RA.

Change in parents' HPV vaccine intentions (Aim 2) will be collected through the iPad application.

### Project Timeline

Project Timeline	Year 1				Year 2				Year 3				Year 4				Year 5			
	Q1	Q2	Q3	Q4																
IRB & staff training																				
Advisory Committee meetings																				
Meetings with communication consultant, [name]																				
Build study database & CATI software for surveys																				
Build, pretest, refine, & tech support for the self-persuasion tablet																				
Use EMR to identify eligible patients for each stage																				
Stage 1: Define intervention content (Aim 1)																				
Conduct cognitive interviews of self-generated arguments (n=50)																				
Transcribe recordings and code interview data																				
Clinic launch meeting for recording discussions																				
Recruit & audiorecord parent-provider discussions (n=50)																				
Apply [name]'s coding scheme to transcribed data on discussions																				
Stage 2: Optimize intervention's effects (Aim 2)																				
Refine tablet program for 4 self-persuasion intervention conditions																				
Recruit & conduct proof of concept study (n = 160)																				
Analyze & synthesize quantitative and qualitative data																				
Select self-persuasion intervention condition for Stage 3																				
Stage 3: Assess feasibility in safety-net clinics (Aim 3)																				
Clinic launch meeting for pilot RCT																				
Conduct pilot including audiorecord discussions (n =90)																				
Code parent-provider discussions																				
Analyze data & publish manuscripts																				

### Data Management

Drs. [name] and [name] will oversee the data collection process. A Microsoft SQL Server database stored on a secure UTSW server and accessed with a Microsoft Access Data Project user interface will house the data. Several procedures will be used to maintain data integrity and ensure that data shared between Parkland and UTSW are

secure. [name] will conduct audits to assure appropriate safeguards of participant privacy are maintained. Study team personnel will send the MRNs of the most recent subjects randomized who were not eliminated at the clinic visit and were consented back to Parkland so these persons will continue to be included in the reports of study participants.

Drs. [name] and [name] will work with the project manager to oversee the data collection process and training of project staff. Project staff will undergo extensive training, using protocols developed in our prior work. A two-day training session will include: (1) project rationale and overview; (2) detailed information on data collection procedures, (3) training and certification in protection of human subjects, confidentiality and HIPAA regulations, and (4) role playing for administering interviews or hands-on practice in retrieving records data, depending on job description. Telephone interviews will be digitally recorded for quality assurance; all recordings will be reviewed during the first two weeks and a random sample will be reviewed thereafter.

For a description of the statistical analyses, see Biostatics section.

## Criteria for Inclusion of Subjects

The intervention target for this study are undecided parents of adolescent patients aged 9-17 who have not started the HPV vaccine series and are receiving primary care through Parkland's neighborhood- and school-based clinics. All research procedures will be conducted with the parents of adolescent patients. Adolescent patients themselves are only indirectly exposed to research procedures because we will access their EMR data for recruitment and to track subsequent vaccination, and by virtue of being the adolescent being present at a medical visit during which the parent-provider discussion may be recorded.

To ascertain eligibility, we will use the adolescent's Parkland electronic medical record (EMR) to determine age, HPV vaccine status, and clinic site. We are requesting a waiver of HIPAA authorization to review the EMR for recruitment purposes only. Parents/ guardians of eligible adolescent patients will be invited and verbal informed consent will be obtained during the recruitment telephone call (except in the case of Aim 3, which will be obtained in-person). Child assent for EMR review is not necessary with parent consent. Informed consent process and documentation will clearly explain to parents that their participation in the research protocol involves data abstraction from their child's EMR related to HPV vaccination. In Aims 1b and 3, parents are asked for informed consent to record parent-provider discussion within the medical visit, and will be informed that comments made by their child during this same interaction could be captured.

Parents enrolled in Aim 2 (proof-of-concept study examining the 4 self-persuasion intervention conditions) may opt for their adolescent child to receive the first dose of the HPV vaccine during the research study visit at the Parkland clinic where the appointment will occur; vaccine administration is not a required research procedure. Appointments will occur during clinic hours where vaccine administration from a Parkland nurse is available as a part of usual care. We include this option to facilitate delivery of care at the request of Parkland Health & Hospital System and for the following reasons. Receipt of the HPV vaccine series is concordant with clinical guidelines for this age group, all immunizations administered to children under age 18 requires parental consent, and HPV immunization is standard of care at Parkland (providers have standing orders to administer this vaccine).

## Criteria for Exclusion of Subjects

Age was restricted to 9-17 based on clinical guidelines and eligibility for free vaccines through the VFC program (i.e., eliminating cost as a barrier), and parental consent being required for vaccines. We will exclude pregnant adolescents due to contraindication and parents who do not provide informed consent, lack telephone access, or have impaired hearing or speech (i.e., cannot complete study activities). Parents who participate in Stage 1 or 2 will be excluded from later stages.

For Aim 2 and Aim 3, we will select adolescents who have been seen or those with upcoming appointments at any of the Parkland neighborhood and school clinics. Table 3 summarizes the inclusion and exclusion criteria for the study.

## Table 3. Inclusion and exclusion criteria and methods of ascertainment

Eligibility Criteria	Ascertainment Method
Inclusion	
Age 9-17 years	EMR audit
Visited clinic in past 18 months	“ “ (except CRR¥)
Have not started HPV vaccine series*	“ “
Undecided about the vaccine	Phone call
Exclusion	
Pregnancy of the adolescent	EMR audit
Sibling already enrolled in project	EMR audit/phone call
No access to a telephone	“ “
Does not give informed consent	Phone call/ clinic visit
Impaired hearing or speech of parent	“ “
Participation in earlier stages	Study database

\*In Aim 1a, we will recruit 11 parents of adolescents who have been immunized to capture the full range of pro-vaccine arguments.

¥ The participants taken from the Community Research Registry will not have the requirement of a clinic visit in the past 18 months.

## Sources of Research Material

Quantitative data will be extracted from the Parkland electronic medical record (EMR) by programmers, provided to the Principal Investigators and cleaned, recoded, and analyzed by research staff to: 1) facilitate study recruitment and 2) to assess HPV vaccine status after exposure to the intervention (Aim 3). Additional quantitative data will be collected from parent participants' responses to baseline and exit surveys (Aims 1, 2, and 3).

Qualitative data will be drawn from audio-recordings of participants' self-generated arguments (Aim 1a), audio-recordings of parent/provider interactions (Aims 1b and 3), and responses to open-ended interview questions in the exit survey after exposure to one of the 4 intervention conditions comparing levels of choice and cognitive processing (Aim 2).

## Recruitment Methods and Consenting Process

We are requesting a waiver of HIPAA Authorization to identify patients who are eligible to be approached with requests to participate in the study (Aims 1, 2, 3). Such a waiver is justified because: minimal risk is anticipated; the waiver will not adversely affect the rights and welfare of subjects; and this aspect of the project cannot be practically conducted without waiver.

We are also requesting a waiver of documentation of consent for study procedures involving clinicians. For parent surveys and interviews, verbal consent and verbal HIPAA authorization will be requested. Token gift cards will be provided to participants as an acknowledgment of their time and effort. All data will only be accessible to authorized study personnel.

**Parents:** Eligible participants will include parents of female and male Dallas county residents ages 9 to 17 years old who receive primary care at a Parkland neighborhood or school-based clinic. We will exclude patients who have already received at least one dose of the HPV vaccine. We will also exclude patients who have not been seen within the past 18 months. For the cognitive interview stage only, we will also recruit participants from the Community Research Registry using the same eligibility criteria above, with the exception of having to receive a primary care visit at a Parkland neighborhood or school-based clinic.

Patients will be identified through EMR review, by ICD-9 or procedure codes, through HIPAA-compliant methods, which will enable our team to invite patient parents with the permission of the Parkland Medical Director ([name]). Parents of patients will be mailed an invitation letter on Parkland letterhead and signed by Drs. [name] and [name] requesting participation in a "study to improve patient satisfaction with healthcare and delivery of vaccines/shots." The letter will provide a telephone number parents can use to ask questions or notify staff of refusal. Letters will be sent in English or Spanish based on the family's preferred language listed in the EMR.

Following the mailing, parents of patients who have not refused contact will be called by a bilingual research assistant (RA). The RA will explain the project and screen parents for eligibility. The RA will screen parents by asking: 1) if their child has ever had the vaccine (yes/no), 2) whether they had ever heard of the vaccine (yes/no),

and 3) what best describes their thoughts about it (never thought, undecided, do not want, or do want). Parents who are undecided or never thought about the vaccine will be invited. If the parent agrees, the RA will obtain verbal consent, administer the baseline survey, and arrange to meet the parent at either UT Southwestern Medical Center (Aim 1a), a Parkland clinic at a chosen time (Aim 1a and Aim 2), or a Parkland clinic prior to an upcoming appointment (Aims 1b and 3). Up to 6 contact attempts (3 day, 3 night) will be made. Based on data from previous projects, we expect 6-8% will actively refuse, 13-15% will have a non-working number, and 20-22% will be unreachable. For Aim 3, parents will be sent a letter, and eligibility will be determined in-person before the child's upcoming medical appointment. Eligibility criteria for Aim 3 will be determined by asking the parent if their child has ever had the HPV vaccine (yes/no). If never had the vaccine, the parent will be invited in-clinic that day and consent will be obtained.

During the study appointment, a bilingual RA will 1) obtain HIPAA authorization to review the adolescent patient's EMR, and 2) instruct the participant on how to use either the English or Spanish version of the tablet application. For Aims 1a and 2, the study appointment will last about 60 minutes and will be audio-recorded. For Aims 1b and 3, pre-clinic visit study activities will take 10-20 minutes; post-visit activities will take another 20-25 minutes. All study staff will be trained by Drs. [name] and [name]. Parent participants will receive a \$50 honorarium in the form of a gift card.

We will conduct study visits with a total of 369 parent participants. We expect very few parents will be fathers (<5%; n = 19) and have powered our analysis to only analyze data from mothers of adolescent patients (n = 350). For Aim 1, we will enroll 106 parents: 53 for formative research on self-generated arguments (Aim 1a), and 53 to characterize parent-provider discussions about the HPV vaccine (Aim 1b). For Aim 2, 168 parents will be enrolled for self-persuasion intervention conditions comparing levels of choice and cognitive processing. We will enroll 95 parents for Aim 3, recording provider/patient interaction and testing of tablet-based application. We expect to enroll 18 providers in order to audiorecord the parent-provider discussions for Aims 1b and 3.

**Providers:** Subject identification and recruitment is based on professional role and job responsibilities related to the HPV vaccination process. The study purpose and objectives will be explained during an introductory clinic site visit. Ample opportunity for clarification and opt-out will be provided. Oral consent will be requested in advance, with a written information sheet explaining the study purpose and aims, in order to minimize disruption of work. Parkland's Medical Director, [name], will endorse and initiate all participant invitations. We estimate that up to 18 providers at the neighborhood and school clinics will choose to participate.

Any and all personal identifiers will be removed from transcripts of the appointment recording, in addition to usual data protection safeguards. Other members of the research team will only have access to de-identified materials. Audiorecordings and transcripts are exchanged through an encrypted, account-specific, password-controlled FTP site.

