### In addition to their adolescents receiving usual care, all parents in this study will be:

- a) Mailed an invitation letter describing the study;
- b) Called to verbally describe study, invite to participate, and confirm willingness to come to an in-person meeting; and
- c) Asked to complete a baseline survey during/after the recruitment call, except for Stage 3, when parents will not complete the baseline survey and will be approached in-person instead of by phone to obtain consent and verify eligibility

**Parents enrolled in Aim1a will be** asked to generate pro-vaccine arguments after using a tablet-based application that provides HPV vaccine information suited for parents of adolescent females & males.

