### **Aim 3. Examine feasibility of the optimal intervention (identified in Aim 2) with a pilot study (n = 90) in the safety-net clinics.**

**Analysis Plan for Aim 3:** We will obtain information on the following outcomes that will be important for developing a subsequent efficacy randomized controlled trial (RCT).

**Enrollment rates.** We will assess whether enrollment rates are similar across the clinic sites.

**Sufficient time for intervention procedures.** Because clinic sites may differ in their patient flow and visit wait times, we will track the number of participants who complete the tablet-based procedure within the time constraints allowed by the clinic and determine whether time allotted for completing the intervention is similar and sufficient across all sites. We expect an 85-90% completion rate to determine feasibility.

**Potential for contamination.** We will determine the appropriate level of randomization (patient, provider, or clinic) and the degree to which contamination occurs at each level. We will use visit history data in the EMR to examine the percentage of patients who visit more than one clinic and see more than one provider. For example, if there is significant crossover of patients to different providers at the same clinic, then we will randomize at the clinic-level in the subsequent efficacy trial.

**Intermediate outcome – active parent participation.** We hypothesize that exposure to the self-persuasion intervention will positively influence active parent participation in discussions with providers. We will apply [name]'s scheme to code the 3 types of active communication (Aim 1b). To estimate effect sizes for the subsequent efficacy RCT, we will compute means, standard deviations, and ranges of parent and provider communications and compare them to data collected in Aim 1b. We will use multivariable mixed linear regression modeling to explore factors associated with parent degree of participation (e.g., English vs. Spanish language). This method models the provider as a random effect to adjust for potential clustering of patients by provider; parent/patient characteristics of interest will be modeled as fixed effects.

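### The documents conflict on whether Aim 3 is limited to undecided parents and has a baseline survey; under the in-clinic rule, stance before randomisation goes unrecorded

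*Combined protocol and SAP*

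**What the plan says.** **Who is eligible.** Criteria for Inclusion of Subjects states: "The intervention target for this study are undecided parents of adolescent patients aged 9-17 who have not started the HPV vaccine series". Table 3 lists "Undecided about the vaccine" as an inclusion criterion, ascertained by phone call. Its two footnotes cover Aim 1a and the Community Research Registry; neither covers Aim 3. Criteria for Exclusion of Subjects discusses selection for Aims 2 and 3 and then points to Table 3 as the study's criteria.

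The phone screen in Recruitment Methods and Consenting Process includes a stance item with four answers (wants the vaccine, does not want it, undecided, never thought about it). Only parents giving the last two answers are invited. They then complete the baseline survey, and a meeting is arranged at one of several places, including "a Parkland clinic prior to an upcoming appointment (Aims 1b and 3"). Later in the same paragraph, Aim 3 gets its own rule: "Eligibility criteria for Aim 3 will be determined by asking the parent if their child has ever had the HPV vaccine (yes/no"). A parent who answers no is invited and consented that day. Study Procedures carries the same text.

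**Baseline survey.** The Study Procedures list for all parents includes it "except for Stage 3, when parents will not complete the baseline survey and will be approached in-person instead of by phone". Measurement of Primary Outcomes gives it to all 369 parents "after or at the end of the recruitment call by a trained research assistant (RA), except for Aim 3 participants". Sources of Research Material lists "responses to baseline and exit surveys (Aims 1, 2, and 3").

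**Use of the pilot.** The Aim 3 analysis plan uses the uptake effect to inform the design and size of a later efficacy trial. The end of Background and Potential Benefits both place that trial in undecided parents. For communication outcomes, "we will compute means, standard deviations, and ranges of parent and provider communications and compare them to data collected in Aim 1b". Intentions, benefits and barriers are also to be measured in Aim 3, with no time point given.

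**The concern.** Staff cannot follow all of these instructions. Under the in-clinic rule, parents who already want the vaccine and parents who have already refused it can both enter Aim 3, and nothing planned before randomisation would identify them. Two uses of the data are affected.

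- **Planning the next trial.** The pilot effect would come from all parents of unvaccinated children, while the next trial is for undecided parents. If decided parents respond less, the pilot understates the effect in the target group. Without a stance record, that effect can be neither estimated nor adjusted for, and the record cannot be rebuilt after exposure to the intervention.
- **The comparison with Aim 1b.** Aim 1b parents pass the stance screen and Aim 3 parents need not. A difference in communication scores would mix the intervention with a difference in who was enrolled.

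**Working it through.** **1. The sections side by side**

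| Question | One reading | Other reading |
|---|---|---|
| Aim 3 limited to undecided parents? | Yes: Criteria for Inclusion; Table 3; phone-screen sequence naming Aim 3 | No: one-question in-clinic rule, stated in Study Procedures and in Recruitment Methods |
| Table 3 method (phone call) usable in Aim 3? | Implied by Table 3 | No: Stage 3 parents are approached in person |
| Aim 3 baseline survey? | Yes: Sources of Research Material; phone-screen sequence | No: Study Procedures; Measurement of Primary Outcomes |

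**2. The plan's own count.** 53 + 53 + 168 + 95 = 369 reproduces the stated total, and 48 + 47 = 95 reproduces the Aim 3 total. The baseline survey figure of 369 therefore includes the Aim 3 parents whom the same sentence excepts. Without them it is 369 − 95 = 274; the 95 are 25.7% of the total.

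**3. Dilution of the effect (assumed inputs).** The documents give neither the stance mix nor effects by stance. Let u be the share undecided or never having thought about it, and r the effect in decided parents relative to that in the undecided. The all-comer difference is f = u + (1 − u)r times the undecided difference. With similar variance, the sample size planned from it changes by 1/f².

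| u | r | f | 1/f² |
|---|---|---|---|
| 0.70 | 0 | 0.70 | 2.04 |
| 0.70 | 0.5 | 0.85 | 1.38 |
| 0.50 | 0 | 0.50 | 4.00 |
| 0.50 | 0.5 | 0.75 | 1.78 |
| any | 1 | 1 | 1 |

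A negative r would dilute further. With r above 1, the all-comer effect would overstate the undecided one.

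**4. Check with explicit rates (also assumed).** Take uptake of 30% vs 45% in undecided parents, 80% in both arms for those who want the vaccine and 5% in both arms for those who do not. With 100%, 80%, 60% and 40% undecided, the pilot difference is 15, 12, 9 and 6 points. At two-sided 5% and 80% power, the implied size per arm is 163, 257, 462 to 482, and 1,050 to 1,088. The ranges reflect how the decided parents split.

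**5. Precision of the pilot.** The Wald 95% half-width is 1.96 × √[p₁(1 − p₁)/n₁ + p₂(1 − p₂)/n₂]. At 60% vs 40%:

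- all parents, 48 vs 47: 0.197
- undecided only, u = 0.70, 34 vs 33: 0.235
- undecided only, u = 0.50, 24 vs 24: 0.277

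**6. What adjusting for stance gains.** Assume 30% want, 50% undecided and 20% refuse, with control uptake of 80%, 40% and 10%, and an effect only in the undecided (40% to 60%).

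- Control: 0.3 × 0.8 + 0.5 × 0.4 + 0.2 × 0.1 = 0.46. Intervention: 0.46 + 0.5 × 0.2 = 0.56.
- The unadjusted variances are 0.46 × 0.54 = 0.248 and 0.56 × 0.44 = 0.246, so the half-width is 0.200.
- The within-stance variance is 0.3 × 0.16 + 0.5 × 0.24 + 0.2 × 0.09 = 0.186 in both arms, so the half-width is 0.173.
- By the arcsine formula at 80% power, n per arm is 97 for 40% vs 60% and 391 for 46% vs 56%. The ratio is about 4, matching step 3 at u = 0.50 and r = 0.

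**7. Chance imbalance.** For a stance category with true share p, the standard error of the difference in shares between arms is √[p(1 − p)(1/48 + 1/47)]. For p from 10% to 50%, the chance of a difference above 10 points is about 10% to 33%. Without the item it could be neither seen nor adjusted for.

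**The case against.** The best defence is that a specific rule overrides general text. Concise Summary of Project also says Stage 3 eligibility is verified at the appointment and not by phone, and two sections expressly drop the Aim 3 baseline survey. The mention of Aim 3 in the phone sequence describes a meeting place, and the in-clinic rule follows shortly after. Criteria for Inclusion speaks of a target, and the list of eligible parents in Recruitment Methods does not mention being undecided. Sources of Research Material may be a collective list. Open enrolment is a legitimate choice for a feasibility pilot.

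Much of this stands as evidence of intent. It does not remove the conflict: Table 3 is then wrong for Aim 3, and no stance item is planned before randomisation.

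The intentions measure could fill the gap if taken in the 10 to 20 minutes of pre-visit activity, but its timing is not stated, and change in intentions collected on the tablet is described for Aim 2 only. The participation model allows for parent characteristics, but stance must be recorded before it can enter.

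Three limits also stand. Every dilution figure rests on assumed inputs. With a half-width of about 20 points, the pilot could not size a trial precisely even with stance recorded. The Aim 1b comparison is non-randomised in any case; stance adds to that limitation. Asking for a stance just before the task might also influence responses, though it would do so in both arms.

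**Conclusion.** The concern holds. The eligibility and baseline survey statements for Aim 3 contradict one another. If the in-clinic rule is the intended one, the pilot enrols a broader population than the trial it is meant to inform, with no planned means of recovering the effect in undecided parents.

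The randomised comparison is not biased and the feasibility outcomes are little affected. The damage is to carrying the effect size over to the next trial and to the Aim 1b comparison. Its size cannot be fixed from the documents. For 50% to 70% undecided and a relative effect of 0 to 0.5 in decided parents, the planned sample size would be about 1.4 to 4 times what the undecided effect implies; with equal effects there is no change. This is worth correcting because the remedy is cheap and the information cannot be collected afterwards.

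**What to change.** Ask the scripted four-answer stance item at in-clinic Aim 3 screening, before randomisation. Then choose one of two routes:

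- **(a)** Restrict Aim 3 to parents who are undecided or have never thought about the vaccine.
- **(b)** Keep open enrolment and add an Aim 3 exception to Criteria for Inclusion and Table 3. Include stance in the uptake, intentions and participation models and in the comparison with Aim 1b. When planning the next trial, report the effect in undecided and never-thought parents with its confidence interval beside the all-comer estimate.

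Under either route, state when Aim 3 intentions are measured, say whether parents who have never thought about the vaccine count as undecided in Table 3, and correct the baseline survey denominator if Aim 3 is excepted. Reconcile Study Procedures, Measurement of Primary Outcomes, Criteria for Inclusion, Table 3, Sources of Research Material, Recruitment Methods and the Aim 3 analysis plan.

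The cost is one question in clinic and some rewording. Route (a) slows recruitment. Route (b) gives an imprecise subgroup estimate (half-width about 23 to 28 points for 70% to 50% undecided), so it should not be the sole planning figure.
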